Study Type: Interventional

Actual Enrollment: 205 participants

Allocation: Randomized

Intervention Model: Parallel Assignment

Masking: Double (Participant, Investigator)

Primary Purpose: Treatment

Official Title: Effects of Carnitine Supplementation on Exercise-Induced Muscle Damage: A Randomized Controlled Trial

Actual Study Start Date: May 9, 2025

Actual Primary Completion Date: May 15, 2025

Actual Study Completion Date: June 5, 2025

METHOD

Participants

This randomized, double-blind, placebo-controlled study was conducted to investigate the effects of L-carnitine supplementation on markers of muscle damage and delayed onset muscle soreness following high-intensity interval training in trained athletes. The study was reported in accordance with CONSORT guidelines for randomized controlled trials. The exercise protocol, anthropometric measurements (and supplement protocol of the study were carried out by the researchers at the Exercise Laboratory of Istanbul Sabahattin Zaim University Faculty of Sports Sciences. The study consisted of two stages. On the first day of the visit ([Figure 2](#)), the participants' height (Tarti Telescopic Height Meter) and weight (Tanita MC 780 ST Black) measurements were determined. In the next stage, before the supplementation period, resting venous blood samples of the participants were taken from the antecubital vein by a specialist nurse working at Istanbul Sabahattin Zaim University Health Unit. Following the

blood collection process, the randomization processes of the participants were carried out. For this purpose, written numbers from 1 to 24 were placed inside a box in a way that the participants could not see, and the participants were asked to choose one of the numbers at random, accompanied by an independent observer other than the researcher. This process was recorded by the observer both on the survey form and digitally. The second day of the visit took place after a 21-day reinforcement period ([Figure 2](#)), blood samples were collected from the participants by a healthcare professional at rest, 2 h, 24 h, 48 h and 72 h after exercise, and were centrifuged by the researcher and stored at -20 degrees.

[figure not shown]

Figure 2. Experimental Design Scheme for conducting the study

High-Intensity Interval Training Protocol

During the pre- and post-supplementation period, participants performed a high-intensity interval training protocol to exhaustion on a Wingate-based cycle ergometer (Monark 894E) at a workload of 0.75 g/kg watts, consisting of 30-s bouts of work divided by 4-min recovery intervals ([Figure 2](#)). Blood samples were taken from the fingertip to measure blood lactate levels immediately before the test and at the 1st, 3rd, 5th, 7th, 9th and 11th minutes after the end of the test. A lactate analyzer (LactateScout (+)) was used to measure blood lactate levels. In addition, participants were asked to rate the feeling of fatigue they felt on the Borg Scale

(BorgScale 6-20) to determine the exercise intensity level at the end of each HIIT set ([Figure 2](#)).

Supplementation Protocol

Although the optimal dose and form of L-carnitine administration are unclear, in a review article examining the pharmacokinetics of L-carnitine, the Alsuntanged Group (2020) and Evan and Fornasini (2003) reported that L-carnitine would be relatively ineffective in increasing plasma levels unless doses of 2–4 g were used daily due to its low bioavailability [36,37]. Additionally, pharmacokinetic data support the administration of multiple daily doses of LC. Therefore, in our study, participants in group LC were given 3 g/day of supplementation (1 g LC capsules three times daily at 8-hour intervals) for 3 weeks (SepeNatural, L-Carnitine L-Tartrate, China). The product contains L-carnitine (% 68), L-Tartaric acid (% 31) and a very small amount of chloride. This carnitine dose was chosen to maximize plasma carnitine concentrations without exceeding the renal threshold for carnitine [29]. The PLS group was given powdered sugar at the same rates and intervals (1 g CHO capsules three times daily at 8-hour intervals). The usage instructions for each participant were written inside the numbered boxes. The capsules containing L-carnitine and placebo to be given to the participants were filled manually by the researcher using a precision scale (Neck; MH 3000 Model, 0.01 Gr sensitivity). All capsules belonging to the PLS and LC groups had the same appearance, color and dimension. During the study, the researcher made reminders every 8 hours via WhatsApp to monitor the participants' use of carnitine and placebo, and additional precautions were taken with alarms set by the participants every 8 hours. The products used in each session were taken after a full stomach. Additionally, no adverse effects related to the supplement were reported by the participants in this study.

Determination of Muscle Pain Sensation

Muscle pain sensation in the leg extensor and leg flexor muscles was determined using the Numbered Pain Rating Scale (NPRS), one of the most widely used scales due to its simplicity and practicality [38-40]. The NPRS is a scoring method where a score of zero represents no pain and a score of 10 represents maximum pain. While the NPRS has been validated on numerous patients as a measurement tool for pain intensity [41], its use as a screening tool has not yet been tested [41]. In the application, the patient is asked to rate the severity of their pain. This score is used as the pain score. In this study, we classified the scale scores as mild (1-3), moderate (4-6), or severe (7-10) as previously described [39,42]. Following 21 days of supplementation, participants were asked to quantify their pain sensations using the NPRS

during blood sample collection at 2, 24, 48, and 72 hours after the HIIT protocol. Feedback from participants was recorded on the questionnaire by the supervisor.

Blood Sampling and Analysis

Total carnitine blood sample was collected from the antecubital vein at rest before the 21-day LC supplementation period by a specialist nurse at Istanbul Sabahattin Zaim University Health Unit, as well as immediately before HIIT and at 2 hours, 24 hours, 48 hours and 72 hours after HIIT following the 21 days of supplementation (CK,LDH,). The collected blood samples were kept at room temperature for approximately 30 minutes and then centrifuged at +4°C, 3000 rpm, for 20 minutes using a centrifugal machine (Hitachi Koki Himac CR22N High-Speed Refrigerated Centrifuge, cCS Aus model/913350C2). After the centrifugation process, the transparent liquid remaining in the tube was transferred to 2 ml Eppendorf tubes, then stored at -20 C and analyzed in the laboratory. In addition, following 21 days of supplementation period, blood lactate levels were determined from the fingertip immediately before the HIIT test and at the 1st, 3rd, 5th, 7th, 9th and 11th minutes after the end of the test.

Human Total Carnitine Measurement from Serum

Total carnitine levels in serum samples were measured using a Human Total Carnitine ELISA kit (Bioassay Technology Laboratory, Shanghai, China). Absorbance readings were obtained with a Chromate 4300 microplate reader (Awareness Technology, Inc., [name]). Results were expressed in nmol/ml. Data were calculated using linear regression, with absorbance measured at 450 nm.

Measurement of CRP, CK, LDH and Uric Acid

Serum CK and LDH were analyzed on a fully automatic analyzer (Roche Cobas Integra 400 Plus, Roche Diagnostics GmbH, Mannheim, Germany) using ROCHE kits (Mannheim, Germany).

Statistical Data Analysis

Data obtained using a double-blind placebo control group experimental design was analyzed using SPSS 25.0 statistical software. The analysis process began by assessing whether the data exhibited a normal distribution. Normality of the data was assessed using the Shapiro–Wilk test, as well as skewness and kurtosis values. Homogeneity of variances was examined using Levene’s test. A two-way repeated measures ANOVA (condition × time) was performed to

determine the effects of L-Carnitine (LC) and placebo (PLS) supplementation on BMI, body fat percentage, lean body mass, resting heart rate, blood lactate concentration, delayed onset muscle soreness (DOMS), and muscle damage markers (CK, LDH) across different time points. When significant main or interaction effects were found, pairwise comparisons were conducted using the Bonferroni post-hoc test. All data are presented as mean \pm standard deviation (SD). Statistical significance was accepted at $p < 0.05$.

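### The text does not settle whether a pre-supplementation lactate series exists; if it does, the two-way ANOVA has no session term and gives that series no role as a baseline

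*Combined protocol and SAP*

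**What the plan says.** Four places bear on this.

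- **High-Intensity Interval Training Protocol.** "During the pre- and post-supplementation period, participants performed a high-intensity interval training protocol to exhaustion". A separate sentence places fingertip lactate "immediately before the test and at the 1st, 3rd, 5th, 7th, 9th and 11th minutes after the end of the test". That makes seven samples, and no session is named.
- **Method, design description.** "On the first day of the visit", height and weight were measured. Next, "before the supplementation period, resting venous blood samples of the participants were taken from the antecubital vein". The number draw comes after that, following the "blood collection process, the randomization processes of the participants were carried out". No exercise test or lactate sampling is listed for this visit. Post-exercise blood sampling appears only at the second visit, after 21 days.
- **Blood Sampling and Analysis.** The same seven lactate times are given, dated to one occasion: "following 21 days of supplementation period, blood lactate levels were determined from the fingertip immediately before the HIIT test", and then the same six minutes after the test.
- **Statistical Data Analysis.** "A two-way repeated measures ANOVA (condition × time) was performed" for a list of outcomes that includes blood lactate. The section gives no time levels for any outcome, no session factor and no baseline covariate.

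**The concern.** Someone analysing lactate from this text cannot tell whether each participant has seven values or fourteen. That decides what the time factor means. With one series, time is minutes around a single test. With two, time has two parts, the session (before or after supplementation) and the minute within it, and the stated model names only one time factor.

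It also decides what can be concluded. A pre-supplementation exercise response would be the natural baseline for lactate, and the stated plan gives it no role. Without one, the sample taken just before the test is itself a post-supplementation value, so change within a person from before supplementation cannot be estimated.

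**Working it through.** The plan states no figure for this point, so there is none to reproduce. The check compares the sections and then counts what each reading implies.

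**Step 1. Three readings of the schedule**

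| Reading | HIIT section | First-visit account | Blood Sampling section |
|---|---|---|---|
| A. HIIT and lactate before and after | fits; natural reading of the lactate sentence | omits the first session | omits the first series |
| B. HIIT before and after, lactate after only | fits, since the lactate sentence names no session | omits the first session | fits |
| C. HIIT and lactate after only | conflicts with the opening sentence | fits | fits |

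Reading B agrees with every affirmative statement. Reading A agrees with them too, but needs two sections to be incomplete. Reading C requires the HIIT sentence to be wrong. The text alone does not choose among them.

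**Step 2. What each reading means for the ANOVA**

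Inputs: 2 arms; 7 samples per series (HIIT section; Blood Sampling and Analysis); significance level 0.05 with Bonferroni post-hoc tests (Statistical Data Analysis). For error df only, N = 24 is used as an illustration, from the 24 numbers in the draw. The registry header gives an enrolment of 205; that discrepancy is a separate matter.

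Formulas for L time levels: interaction df = (2 − 1)(L − 1); error df = (L − 1)(N − 2); pairwise time contrasts = L(L − 1)/2; Bonferroni threshold = 0.05 ÷ contrasts.

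- **One series, L = 7:** interaction df 6; error df 6 × 22 = 132; contrasts 7 × 6/2 = 21; threshold 0.05/21 = 0.00238.
- **Two series run together as one factor, L = 14:** interaction df 13; error df 13 × 22 = 286; contrasts 14 × 13/2 = 91; threshold 0.05/91 = 0.00055.
- **Two series with session as its own factor:** condition × session, 1 and 22 df; condition × session × minute, 6 and 132 df. This is a three-factor model, not the stated two-way one.

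The 13 df in the second case are 1 (condition × session) + 6 (condition × minute) + 6 (three-way). One omnibus test would pool three different questions.

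**Step 3. What a baseline would be worth, if recorded**

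Let r be the correlation between a participant's pre- and post-supplementation lactate. Adjusted between-person variance = (1 − r²) × unadjusted variance. The documents give no r, so a range is assumed. The power columns also assume the effect size, equal arms, a two-sided 0.05 test and a normal approximation. The two sizes, 12 and 102 per arm, come from halving 24 and about halving 205.

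| r (assumed) | Variance left | Power, 12 per arm, 0.8 SD | Power, 102 per arm, 0.3 SD |
|---|---|---|---|
| no adjustment | 1.00 | 50% | 57% |
| 0.3 | 0.91 | 54% | 61% |
| 0.5 | 0.75 | 62% | 70% |
| 0.7 | 0.51 | 78% | 85% |

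These gains apply to the between-arm comparison of lactate. The condition × time interaction is tested against within-person error, and a single covariate that is constant over minutes does not reduce that error.

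**The case against.** The strongest defence is that no section denies a first HIIT session, and none says that lactate was taken twice. The only dated lactate series is the one after supplementation, its seven times are listed identically in two sections, and a condition × time model with seven levels fits it directly. Figure 2 is cited for both visits and for the HIIT sentence. It could not be seen here and may settle the schedule. All of this stands, and it rules out several stronger readings that a reader might infer:

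- *The sections flatly contradict each other on lactate.* They do not. One affirms a pre-supplementation HIIT session; the others leave it out.
- *The lactate time factor is undefined.* The minutes within a test are defined. What is open is whether time also spans two sessions.
- *A two-way model could never separate session from minute.* A 14-level factor contains every session-by-minute cell, so planned contrasts could separate them. The plan specifies none.
- *Without a baseline, no effect of supplementation can be claimed.* In a randomized trial, a difference between arms after supplementation can support an effect. Only within-person change from before supplementation is out of reach.

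The defence does not remove the mismatch between the HIIT sentence and the visit-by-visit account. Nor would the figure supply the lactate time levels, session term or baseline rule missing from Statistical Data Analysis.

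**Conclusion.** The point holds as a gap in the schedule with a conditional consequence for the analysis. The text does not establish whether pre-supplementation lactate exists. If there is only the post-supplementation series, the stated ANOVA suits it (7 levels, 6 interaction df), and what needs care is the wording of the schedule and of the conclusion. If two series exist, the stated model lacks a session term and leaves the baseline unused. The cost is then about 25% of between-person variance at r = 0.5 or 49% at r = 0.7, for the between-arm comparison only. Both correlations are assumptions.

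The severity is modest. The stated aim is muscle damage and soreness; lactate is a named ANOVA outcome but lies outside that aim. Post-exercise CK, LDH and soreness are clearly scheduled after the 21 days, and nothing here affects them.

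**What to change.** 1. Reconcile the HIIT section, the first-visit account and Blood Sampling and Analysis to one schedule, consistent with Figure 2. State whether a pre-supplementation HIIT session took place, whether lactate was sampled at it, and whether it came before or after the number draw.
2. In Statistical Data Analysis, list the lactate time levels.
3. **If pre-supplementation lactate was recorded:** analyse post-supplementation lactate by condition and minute, adjusting for the participant's own pre-supplementation lactate. If the condition × minute interaction is the target, use minute-matched baselines or a covariate-by-minute term. Label the analysis as a post hoc change, since the registry header gives the study as completed on June 5, 2025, and report the originally stated model beside it.
4. **If it was not recorded:** correct the text, keep the seven-level model, and limit the lactate conclusion to the randomized comparison between arms after supplementation. Make no claim of within-person change from before supplementation.

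The cost is a text correction in either case. Under item 3 it adds one adjusted model on data already held; under item 4 there is no new analysis. Neither needs new data collection.

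### No means of eliciting adverse events is described, so the safety sentence shows only that none was reported as supplement-related; it is not evidence of tolerability

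*Combined protocol and SAP*

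**What the plan says.** The only safety statement is the last sentence of Supplementation Protocol: "no adverse effects related to the supplement were reported by the participants in this study". It carries two qualifiers, that the effects be related to the supplement and that they be reported. It gives no denominator.

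The contacts at which an adverse event could have come to light are these:

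- **During supplementation** (Supplementation Protocol): dosing was "1 g LC capsules three times daily at 8-hour intervals) for 3 weeks", and "the researcher made reminders every 8 hours via WhatsApp to monitor the participants' use of carnitine and placebo". The stated purpose is capsule use.
- **During exercise** (High-Intensity Interval Training Protocol): "participants were asked to rate the feeling of fatigue they felt on the Borg Scale" at the end of each set. Fingertip lactate was sampled for 11 minutes afterwards.
- **After exercise** (Determination of Muscle Pain Sensation): "participants were asked to quantify their pain sensations using the NPRS", and this was done "during blood sample collection at 2, 24, 48, and 72 hours after the HIIT protocol". The section adds that "Feedback from participants was recorded on the questionnaire by the supervisor"; the questionnaire's items are not listed.
- **Venous draws** (Blood Sampling and Analysis): before supplementation, immediately before HIIT, and at 2, 24, 48 and 72 h.

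Statistical Data Analysis covers body composition, resting heart rate, lactate, soreness, CK and LDH. It includes no adverse-event outcome.

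**The concern.** A count of zero means something only if it is known how events were looked for. Here the count passes through two filters: the event had to be reported by a participant, and it had to be classed as related to the supplement. The documents describe neither the asking nor the classing.

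The second filter matters in a double-blind trial. Whoever judged relatedness while masked did not know which capsule was taken, so the attribution is unreliable. A placebo-controlled design does not need it: all events, whatever the suspected cause, can be compared between arms. The sentence gives that advantage away. It also excludes by definition events put down to exercise to exhaustion or to the six venous draws.

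Readers may take the sentence as evidence that three weeks of L-carnitine was well tolerated. Events that were never recorded cannot be recovered at analysis.

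**Working it through.** The documents give no adverse-event rate, bound or safety sample size, so there is no stated figure to reproduce. The check has two parts.

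**1. Ascertainment, by reading each contact.**

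| Contact | What is described as asked or recorded | Adverse-event question described? |
|---|---|---|
| WhatsApp reminder every 8 h for 21 days (3 × 21 = 63 scheduled doses) | Capsule use | No |
| Each HIIT set | Borg 6–20 rating | No |
| 2, 24, 48 and 72 h after HIIT | NPRS leg pain, on a questionnaire with unlisted items | No |
| Six venous draws | Blood sample | No |

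No definition, recall period, relatedness assessor or table by arm is described.

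**2. What zero events could show, by arithmetic.**

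Inputs:

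- The study-design paragraph of the Method says "written numbers from 1 to 24 were placed inside a box". The allocation ratio is not stated there, so 12 per arm is an assumption.
- The header record gives 205 enrolled. With an equal split (assumption), 205 / 2 = 102.5, taken as 102 per arm.

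Exact upper bound for 0 events in n, assuming every event is captured: 1 − 0.05^(1/n) one-sided, and 1 − 0.025^(1/n) two-sided.

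- n = 12: 1 − 0.05^(1/12) = 22.1%; 1 − 0.025^(1/12) = 26.5%.
- n = 102: 1 − 0.05^(1/102) = 2.9%; 1 − 0.025^(1/102) = 3.6%.

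If only a share s of events is reported, the chance of zero reports at a true rate p is (1 − p·s)^n, and the one-sided bound on the true rate is the bound above divided by s. The documents give neither p nor s. The values below are illustrative assumptions, with p = 10%.

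| Share reported, s | Chance of zero reports, n = 12 | One-sided bound, n = 12 | Chance of zero reports, n = 102 | One-sided bound, n = 102 |
|---|---|---|---|---|
| 1 | 0.90^12 = 28% | 22.1% | below 0.1% | 2.9% |
| 0.5 | 0.95^12 = 54% | 44% | 0.5% | 5.8% |
| 0.25 | 0.975^12 = 74% | 88% | 7.6% | 11.6% |

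The first row reflects sample size alone. The lower rows show what incomplete reporting adds.

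**The case against.** The strongest reply is that silence in the text is not proof of absence. The questionnaire's items are not listed, and neither Figure 2 nor the text under Participants was available in the copy read. A symptom question may have been asked. This stands: the most that can be said is that none is described.

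For the same reason, several stronger readings are not supported:

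- A reader might infer that reports were purely volunteered, or that participants themselves decided what was supplement-related. The text states neither.
- A reader might infer that the questionnaire covered pain only. The text mentions it in the pain section but excludes nothing.
- A reader might infer that the trial claims no adverse effects occurred. The sentence claims less, because both qualifiers are present.
- A reader might infer that a serious event during exercise would have gone unrecorded. Research staff ran the sessions, and nothing says such an event would be noted only if the capsule was blamed.

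It is also fair to say that a reported count of zero is zero in each arm. What is missing is the denominators and the events not classed as related, not the split of that count. The zero-event bounds do mainly measure sample size, and they range widely because of the unresolved 205 and 24. Finally, no efficacy analysis is affected.

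None of this supplies a method of ascertainment. If a question was asked, one line saying so would answer that part of the point; relatedness, unattributed events and denominators would still be open.

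**Conclusion.** The point holds in limited form. As documented, the sentence supports only that no effect was reported as supplement-related. It is not evidence of tolerability, because no way of eliciting events is described, no relatedness assessor is given, no safety outcome is planned, and events not attributed to the capsule fall outside it.

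On size, zero events with complete capture is still compatible with a true rate of up to about 22% one-sided (26.5% two-sided) with 12 per arm, or about 2.9% one-sided with 102 per arm. These figures assume equal allocation and depend on which of 24 and 205 is the real denominator. Incomplete reporting would raise them by an amount the documents do not allow one to fix. The ascertainment gap is present under either denominator.

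This should be corrected, but it does not touch the muscle-damage or soreness results.

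**What to change.** **For the completed data.**

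- Reword the sentence so that it claims only what was collected.
- State whether, how and when participants were asked about adverse events, and who judged relatedness. Say that events were not solicited only if the sponsor confirms it.
- Reconcile the 205 enrolled with the 24 draw numbers. Then give all recorded events by arm, whatever the suspected cause, with denominators and an exact upper 95% bound.
- If only supplement-attributed reports were kept, label the bound as applying to reported, attributed effects and not to adverse events in general.

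**For the design or any repeat.** Ask one identical open symptom question in both arms at contacts that already take place: one WhatsApp message a day, and the pre-HIIT, 2, 24, 48 and 72 h visits. Record every event whatever its suspected cause, and tabulate by arm.

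**Cost.** For the completed data, a wording change and a small table. For a repeat, one extra question at existing contacts. The downside is a less favourable safety statement. The trial's completion date has passed, so the added question cannot repair the present data.

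### On the plain reading, CK and LDH are first measured after 21 days of capsules, so the analysis has no enzyme value that the supplement cannot have influenced, although blood is drawn before randomisation

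*Combined protocol and SAP*

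**What the plan says.** The design paragraph of the Method section places a blood draw at the first visit: "before the supplementation period, resting venous blood samples of the participants were taken from the antecubital vein". Allocation comes afterwards, once that draw is done: "blood collection process, the randomization processes of the participants were carried out". No analyte is named there for this sample.

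Blood Sampling and Analysis names one: "Total carnitine blood sample was collected from the antecubital vein at rest before the 21-day LC supplementation period". The same sentence then lists draws "immediately before HIIT and at 2 hours, 24 hours, 48 hours and 72 hours after HIIT following the 21 days of supplementation (CK,LDH". The visit-2 schedule in the design paragraph matches that list: "blood samples were collected from the participants by a healthcare professional at rest, 2 h, 24 h, 48 h and 72 h after exercise".

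The High-Intensity Interval Training Protocol section also describes a bout before supplementation ("During the pre- and post-supplementation period, participants performed a high-intensity interval training protocol to exhaustion"). No CK or LDH sampling is described around it.

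Under Statistical Data Analysis the model is introduced with "A two-way repeated measures ANOVA (condition × time) was performed to", followed by a list of outcomes that includes CK and LDH. Bonferroni pairwise comparisons follow a significant main or interaction effect. No change score, baseline covariate, reference time or primary ANOVA term is stated.

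**The concern.** CK and LDH carry the trial's question about muscle damage. If their earliest value is the pre-HIIT draw, it is taken after three weeks of L-carnitine or placebo and is itself an outcome of treatment. Three things follow.

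- The condition × time interaction, which asks whether the response to exercise differs by arm, cannot see an effect that is the same at rest and after exercise.
- The condition main effect can see it. But if the arms already differ at the pre-HIIT draw, nothing in the data shows whether that is the supplement at work or a difference present before allocation.
- No CK or LDH covariate is available that is safe to adjust for. Adjusting for the pre-HIIT value could take out part of the treatment effect.

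A suitable blood sample was already drawn before allocation, so the gap looks avoidable.

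**Working it through.** **Plan's own figure.** The available text gives no sample size calculation, effect size or SD for CK or LDH, so there is nothing to reproduce.

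**Inputs from the documents.** Five CK/LDH times (pre-HIIT, 2, 24, 48 and 72 h), all after supplementation; two arms; condition × time repeated measures ANOVA; significance at 0.05; 24 numbers in the randomisation box.

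**Assumptions.** 12 per arm (the split is not stated, and the header gives 205 enrolled, which is a separate conflict); normal data with SD 1; within-person correlation r of 0.5, 0.7 or 0.9, equal between all times; L-carnitine lowers all five values by a constant d of 0.8 or 1.2 SD.

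**Step 1: why the shift cancels.** Write the arm difference at time t as D(t). The interaction tests whether D(t) varies over t. If D(t) = d at all five times, every contrast D(t) − D(pre-HIIT) = d − d = 0. The main effect estimates the mean of D(t), which is d. This does not depend on n.

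**Step 2: simulation (4,000 runs per row; percentage of runs with p < 0.05).**

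| r | d | Interaction, 5 times | Main effect, 5 times | Interaction with day-1 value as sixth time | ANCOVA on mean of 5 later values, day-1 covariate |
|---|---|---|---|---|---|
| 0.5 | 0.8 | 5.4 | 68 | 44 | 87 |
| 0.7 | 0.8 | 5.4 | 58 | 69 | 94 |
| 0.9 | 0.8 | 5.1 | 49 | 99.7 | >99.9 |
| 0.5 | 1.2 | 4.7 | 96 | 83 | 99.7 |
| 0.7 | 1.2 | 4.8 | 90 | 97 | 99.9 |
| 0.9 | 1.2 | 5.1 | 84 | 100 | 100 |

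The Monte Carlo standard error at 5% is √(0.05 × 0.95 / 4000) = 0.34 percentage points, so the interaction column is indistinguishable from 5%.

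**Step 3: precision at one time point.** Residual variance after adjustment is 1 − r² of the unadjusted value: 0.75, 0.51 and 0.19 for r = 0.5, 0.7 and 0.9. The unadjusted SE of the arm difference is √(2/12) = 0.408 SD. Power for 0.8 SD is Φ(0.8/SE − 1.96) = Φ(1.96 − 1.96) = 50%. With SE = 0.408 × √(1 − r²) it becomes 62%, 78% and 99%.

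**Step 4: precision for the mean of the four values at 2 to 72 h.** The variance of that mean is r + (1 − r)/4, and adjustment removes r².

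- r = 0.5: 0.625 falls to 0.375, ratio 0.60.
- r = 0.7: 0.775 falls to 0.285, ratio 0.37.
- r = 0.9: 0.925 falls to 0.115, ratio 0.12.

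**Step 5: size of chance imbalance.** With SE 0.408, an arm difference beyond 0.5 SD in either direction before any treatment has z = 0.5/0.408 = 1.22, a probability of about 22%.

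**Step 6: a proportional effect (assumed CK values).** Placebo is 200 at rest and 400 at 24 h; L-carnitine lowers both by 15%, to 170 and 340. The arm differences are 30 at rest and 60 at 24 h. The difference in change is (400 − 200) − (340 − 170) = 30, so the raw-scale interaction keeps 30 of the 60. On a ratio scale, 400/200 = 340/170 = 2.0 and nothing remains, but the plan describes no ratio or log analysis.

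**The case against.** A reader might infer that any resting effect is subtracted from the trial's result and that the trial is therefore biased towards no effect. The documents do not support that. No change from baseline is defined, and the plan acts on main effects as well as the interaction. A constant shift stays in the condition main effect and in the arm difference at every time. Allocation is randomised, so a missing baseline does not by itself bias those comparisons, and the main-effect test already allows for chance imbalance in its error rate. Nor does the plan call the pre-HIIT draw untreated; that label would come from the reader. For a question about the rise caused by exercise, the draw just before exercise is also a natural comparator. Treating the whole 60 in the example as the true effect presumes a target that the documents do not state.

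A reader might also take it as settled that CK and LDH were never assayed on day 1. The sentence in Blood Sampling and Analysis is loosely built: total carnitine is the grammatical subject of all six draws, and the enzymes appear in a bracket at the end that could qualify the whole list. Nothing says that the day-1 sample was not assayed for them, and the design figure, which was not available here, may specify it.

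These objections limit the claim to the interaction term and to the plain reading. They do not supply an untreated CK or LDH value, and they do not restore the lost precision or the missing balance check.

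**Conclusion.** The point stands in a limited form. On the plain reading, no CK or LDH value from before supplementation is documented, and none enters the ANOVA. A resting effect that is constant over the five draws is invisible to the interaction (about 5% rejection whatever its size). It remains detectable in the main effect, in 49% to 68% of simulated runs at 0.8 SD and 84% to 96% at 1.2 SD. A main effect without an interaction would still be hard to interpret, because the one trial at hand cannot show whether the arms differed before treatment. The avoidable loss of precision is 25% to 49% of residual variance at a single time if r is 0.5 to 0.7.

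The cancellation result needs only a constant shift. The percentages rest on 12 per arm, equal correlations and normal data, none of which the documents state. A larger trial would change the power figures but not the cancellation. This is a cheap improvement in precision and interpretation. It does not invalidate the between-arm comparison.

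**What to change.** 1. State whether the day-1 sample was assayed for CK and LDH. If so, use those values; if not, assay the stored day-1 serum on the same analyser with the same kits.
2. Use the day-1 value as the covariate in an ANCOVA comparing the arms on the 2 to 72 h values. Say which term or contrast is the primary test.
3. Report the pre-HIIT value as an outcome, namely the 21-day effect on resting enzymes, and not as an untreated baseline.
4. If no day-1 serum remains, say so and label the pre-HIIT value as on-treatment. The study is complete and the documents do not mention leftover volume, so this may be the only step open.
5. Reconcile the pre-supplementation HIIT bout with the blood schedule, and state whether the day-1 draw came before or after it.

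**Cost.** One extra CK and one extra LDH assay per participant on blood already collected, with no new visit or venepuncture. The day-1 serum will have been frozen about 3 weeks longer than the later samples, equally in both arms. Steps 3 to 5 need only wording.
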